- 6. If a subject prematurely discontinues trial drug, he/she will be asked to remain in the trial, participating in the scheduled trial visits through Week 52. If a subject prematurely discontinues trial drug and does not wish to continue in the trial, he/she will be asked to return for a clinic visit and undergo the Week 52 assessments. Subjects not entering the 52-week **OLE** will return to the clinic 4 weeks after the last dose of trial drug for a Safety Follow-up Visit.
- 7. Informed consent is required prior to performing any assessments, including submission of medical information for central review. Record date and time informed consent was given and who conducted the process on the appropriate source documentation and per required regulations.
- 8. Baseline lung HRCT will be performed only if no previous lung HRCT is available within the last 6 months prior to Screening date. This can be performed any time between the start of the initial 56 days of Screening and must be completed with results from central review vendor prior to Day 1. Confirm enough time for results to be made available from the central review vendor with turnaround time being up to 5 business days for results. Results are required from central review vendor.
- 9. The lung HRCT scan will be performed for all subjects within ±2 weeks of the Week 52/PD Visit. Central review will be performed.
- 10. Histopathology reports used towards IPF diagnosis (if available, but these are not required) will be submitted for central review.
- 11. Subjects will be randomized in a 1:1:1 ratio to receive fipaxalparant (HZN-825) 300 mg QD, fipaxalparant (HZN-825) 300 mg BID, or placebo.
- 12. For subjects who are entering the OLE Phase.
- 13. If SARS-CoV-2 exposure is of clinical concern for any subject, consider using a DLCO up to 6 months before the Screening Visit.
- 14. Perform for WOCBP. Serum pregnancy test at Screening and Week 52 (or as needed). Urine pregnancy tests should also be done every 4 weeks after randomization, which includes both in-clinic testing at scheduled visits prior to dosing (Weeks 1, 4, 16, 28, and 40) and at home (also a ±5-day window) by the subject and reported to the site (Weeks 8, 12, 20, 24, 32, 36, 44, and 48).
- 15. A complete physical examination will be performed, including, but not limited to, cardiac, pulmonary and neurologic assessments.

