6MWT=6-minute Walk Test; DLCO=diffusing capacity of the lungs for carbon monoxide; FVC=forced vital capacity; HRCT=high-resolution computed tomography; hsCRP=high-sensitivity C-reactive protein; K-BILD=King's Brief Interstitial Lung Disease Questionnaire; LCQ=Leicester Cough Questionnaire; L-IPF=Living with IPF; LPAR1=lysophosphatidic acid receptor 1; PBMC=peripheral blood mononuclear cell; PD=premature discontinuation; PK=pharmacokinetic; SF-12=SF-12® Health Survey; W=Week; WOCBP=women of childbearing potential

- 1. Subjects will receive the first dose of open-label fipaxalparant (HZN-825) in the Extension Phase in the clinic. Baseline assessments will be performed prior to dosing.
- 2. Remote (telephone) visit.
- 3. If a subject prematurely discontinues fipaxalparant (HZN-825), he/she will be asked to remain in the trial, participating in the scheduled trial visits through Week 104. If a subject prematurely discontinues fipaxalparant (HZN-825) and does not wish to continue in the trial, he/she will be asked to return for a clinic visit and undergo the Week 104 assessments. Subjects will return to the clinic 4 weeks after the last dose of fipaxalparant (HZN-825) for a Safety Follow-up Visit.
- 4. Informed consent is required prior to performing any assessments in the Extension Phase. Record date and time informed consent was given and who conducted the process on the appropriate source documentation and per required regulations.
- 5. The result will be considered a Baseline value for this Extension Phase.
- 6. Except when strictly unavoidable, the same person should perform the assessment at each evaluation during the trial.
- 7. The HRCT scan should be performed within ±2 weeks of the Week 104/PD Visit.
- 8. The DLCO is required for Week 80 and Week 104/PD Visits.
- 9. Perform for WOCBP. Serum pregnancy test at Week 104 (or as needed). Urine pregnancy tests should also be done every 4 weeks after the Week 52 Visit, which includes both in-clinic testing at scheduled visits prior to dosing (Weeks 52, 56, 68, 80, and 92) and at home (also a ±7-day window) by the subject and reported to the site (Weeks 60, 64, 72, 76, 84, 88, 96, and 100).
- 10. A complete physical examination will be performed, including, but not limited to, cardiac, pulmonary and neurologic assessments.

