## **Design of the Extension Phase of the Trial**

The Extension Phase of the trial is an optional, open-label, repeat-dose, multicenter extension of the Core Phase. Subjects who complete the Double-blind Treatment Period (Week 52) in the Core Phase of the trial may be eligible to enter this 52-week Extension Phase. Subjects entering the Extension Phase will complete the Week 52 Visit, which will be considered Day 1 of the Extension Phase, and will receive their first dose of open-label fipaxalparant (HZN-825) in the Extension Phase at the clinic and return to the clinic for trial visits at Weeks 56, 62, and 68, then every 12 weeks through Week 104. The Week 52 Visit activities will serve as Baseline for the Extension Phase. Subjects will return to the clinic for a Safety Follow-up Visit 4 weeks after the last dose of fipaxalparant (HZN-825).

If a subject prematurely discontinues fipaxalparant (HZN-825), he/she will be asked to remain in the trial, participating in the scheduled trial visits through Week 104. If a subject prematurely discontinues fipaxalparant (HZN-825) and does not wish to continue in the trial, he/she will be asked to return for a clinic visit and undergo the Week 104 assessments.

[figure not shown]
An overview of the Extension Phase trial design is presented in Figure 9.2 and details of trial activities during the Extension Phase are provided in Section 2.2, *Schedule of Assessments During the Extension Phase*.

PRIVATE AND CONFIDENTIAL INFORMATION OF HORIZON THERAPEUTICS IRELAND DAC (A WHOLLY OWNED SUBSIDIARY OF AMGEN INC.)

Page 64 of 153

Fipaxalparant (HZN-825) Protocol: HZNP-HZN-825-303 Version 5.0, Amendment 4

Figure 9.2 Schematic of Trial Design – Extension Phase

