# 9.6.1.5 Exploratory Endpoint Analyses

Exploratory endpoints will be summarized at each time point. The statistical methods for comparisons of each dose regimen of fipaxalparant (HZN-825) to placebo will be analogous to the methods for comparisons of primary and secondary efficacy endpoints. Correlation analysis will be used to assess the relationship between the percent change from Baseline in FVC % predicted and the percent change from Baseline in lung fibrosis scores at Week 52.

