1.1.2. Part 2 (Extension Phase)

The overall objective of the Extension Phase is to investigate the long-term efficacy, safety and tolerability of HZN-825, a selective antagonist of LPAR1, administered at a dose of 300 mg BID to subjects with IPF in a 52-week OLE following completion of the Core Phase of the trial. The dose for the Extension Phase may be modified based on the results of the Core Phase.

Two types of Baseline are defined for the Extension Phase:

- OLE Baseline, defined as the latest measurement prior to the first dose of HZN-825 in Extension Phase
- HZN-825 Baseline, defined as the latest measurement prior to the first dose of study drug (either HZN-825 or Placebo) in the Core Phase

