3.9. Reporting Period

The reporting periods for each phase are defined below. For subjects that entered OLE Phase, both OLE Phase and combined study period will be used in reporting.

Core Phase

Treatment period: time from first dose of study drug intake to 28 days after last dose of study drug intake in the Core Phase.

Study period: time from first dose of study drug intake to the end of Core Phase.

For subjects who entered and took any study drug in OLE Phase, the day of their first dose intake in the OLE Phase marks the end of their Core Phase treatment and study period.

OLE Phase

Treatment period: time from first study drug intake in the OLE Phase to 28 days after last dose of study drug intake in the OLE Phase.

Study period: time from first dose of study drug intake in the OLE Phase to the end of OLE Phase.

Combined Study Period

Treatment period: time from first dose of study drug intake (either HZN-825 or placebo) in the Core Phase to 28 days after the last dose in the OLE Phase.

Study period: time from first dose of study drug intake (either HZN-825 or placebo) in the Core Phase to the end of OLE Phase.

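### For subjects entering the Extension, the Week 52 lung HRCT has two conflicting timing rules: up to 14 days after the visit, and before the first open-label dose given at that visit

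*Protocol*

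**What the plan says.** **Core schedule (Protocol 2.1, footnote 9; repeated in SAP Appendix 12.1).** "The lung HRCT scan will be performed for all subjects within ±2 weeks of the Week 52/PD Visit". There is no exception for subjects who continue into the Extension.

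**First open-label dose (Protocol 9.1, Design of the Extension Phase).** The Week 52 visit is Day 1 of the Extension. Subjects attending it "will receive their first dose of open-label fipaxalparant (HZN-825) in the Extension Phase at the clinic". The same paragraph adds: "The Week 52 Visit activities will serve as Baseline for the Extension Phase".

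**Extension schedule (Protocol 2.2; repeated in SAP Appendix 12.2).** The Week 52 cell of the lung HRCT row carries footnote 5: "The result will be considered a Baseline value for this Extension Phase". Footnote 1 says: "Baseline assessments will be performed prior to dosing". This schedule has its own two-week HRCT allowance, footnote 7, but it is attached to Week 104 only.

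**Definitions (SAP).** Section 1.1.2 gives "OLE Baseline, defined as the latest measurement prior to the first dose of HZN-825 in Extension Phase", which matches Protocol 9.6.2.1. For subjects who take drug in the Extension, Section 3.9 says "the day of their first dose intake in the OLE Phase marks the end of their Core Phase treatment and study period".

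**Visible use of the scan (Protocol 9.6.1.5).** The change in FVC % predicted is to be correlated with "the percent change from Baseline in lung fibrosis scores at Week 52".

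**The concern.** One scan is meant to do two jobs in a subject who rolls over: close the Core Phase and open the Extension. Both jobs need it to precede the first open-label dose, but footnote 9 lets a site book it afterwards and still be compliant.

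Two things are at stake. The first is classification. The programmer would have to decide after the fact whether a late scan is a Core Week 52 value, an Extension baseline, both or neither. The second is exposure. If dates are ignored, a scan reported under placebo could follow up to 14 days of active drug, and one reported under the QD regimen could follow up to 14 days of BID dosing.

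Other Week 52 assessments were protected. Section 2.2, footnotes 11 to 13, state individually that vital signs, ECG and laboratory samples come before the first open-label dose. Section 2.1, footnote 24, separates rollover from other subjects for PK sampling. The HRCT, whose window runs past the visit, has no such statement of its own.

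**Working it through.** The plan states no figure on this point, so there is nothing to reproduce. The check is calendar arithmetic followed by a comparison of the rules.

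**Inputs**
- Week 52 target: Day 365 (SAP Table 1).
- Week 52 visit window: ±7 days (Protocol 2.1).
- HRCT window: ±14 days around the visit (Protocol 2.1, footnote 9).
- First open-label dose: on the day of the Week 52 visit (Protocol 9.1).
- Pre-study scan: up to 6 months before Screening, with Screening up to 56 days (Protocol 2.1 and footnote 8). Six months is taken as 183 days.

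**Step 1: when the scan can fall**
- Visit: 365 − 7 = Day 358 to 365 + 7 = Day 372.
- Scan: 358 − 14 = Day 344 to 372 + 14 = Day 386.
- Relative to the visit there are 14 + 1 + 14 = 29 permitted days, of which 14 (+1 to +14) follow the first open-label dose. A scan on the visit day with no recorded time is assumed pre-dose under SAP 3.6.

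**Step 2: a scan on day +1 to +14 against each rule**
- Protocol 2.1, footnote 9: complies.
- Protocol 2.2, footnotes 5 and 1: fails, because it is a Baseline value obtained after dosing.
- OLE Baseline definition (Protocol 9.6.2.1, SAP 1.1.2): fails, because it is not a pre-dose measurement.
- Core study period (SAP 3.9): outside, because that period ended on the dosing day.
- Assignment to Week 52: not stated. SAP 3.8 tabulates windows for FVC only and leaves the details for other variables to the TLF shells. The FVC rows point both ways: the Core row stops at the Core Phase end date, whereas the HZN-825 Baseline row keeps Week 52 open from Day 324 to Day 421, which would include Day 386.

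**Step 3: what remains as the last pre-dose scan**

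With no unscheduled scan in between, it is the screening or historical one.
- Youngest: (358 − 1)/7 = 51.0 weeks before the first open-label dose.
- Oldest: (372 − 1 + 56 + 183)/7 = 610/7 = 87.1 weeks.

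This matters only if an HRCT change from OLE Baseline is analysed.

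**Step 4: can both timing rules be met?**

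Yes. A scan from day −14 up to pre-dose on the visit day satisfies footnote 9 and footnote 1 together. Restricting the window to that overlap brings open-label exposure before the scan from a maximum of 14 days to 0. Sample size, power and alpha do not change.

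**The case against.** The strongest reply is that the protocol already restricts this scan. Footnote 9 is an outer limit for everyone, and Section 2.2 adds the specific pre-dose rule for rollover subjects. A site that reads both schedules together will scan before dosing. That is fair, and it means a late scan is not simply permitted. But footnote 9 is addressed to all subjects and contains no cross-reference, and the SAP reproduces both schedules without reconciling them. A site working from the Core schedule alone would not see the restriction.

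Three stronger readings are tempting, and the documents do not support them.

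- **About half of rollover scans are affected.** A reader might take 14/29 = 48% from the window. That assumes booking spread evenly over days that footnote 1 excludes. The share could be anything from 0% to 100%, and nothing in the documents narrows it.
- **Affected subjects drop out of the Week 52 HRCT analysis.** SAP 3.9 defines reporting periods and is not a visit-mapping rule for HRCT. The mapping rule sits in the TLF shells, which are not available, and the FVC analogy cuts both ways.
- **The 52-week Extension change in HRCT would really span two years or more.** Step 3 shows how old the fallback scan could be. However, no Extension objective or endpoint that can be read names an HRCT change. Some entries in those lists are blanked out, and blanked text cannot carry the argument.

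It is also true that the consequence is small. Exploratory p-values are not used for inference (Protocol 9.6.1.9), Extension efficacy is descriptive (Protocol 9.6.2.3), and nothing in the documents suggests that 14 days of drug would move a fibrosis score.

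**Conclusion.** The contradiction is real and should be reconciled; its severity is minor. For a subject entering the Extension, a scan 1 to 14 days after the Week 52 visit obeys Section 2.1, breaks Section 2.2, cannot be the OLE Baseline, and lies outside the Core study period. Its status as a Week 52 value is undefined in the SAP text available.

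The size is bounded in time at 14 days of open-label drug before the scan. It is not bounded in number of subjects, which the documents do not allow anyone to estimate. The visible effect is confined to exploratory HRCT work, namely the correlation in Protocol 9.6.1.5. Primary and key secondary FVC results are not affected.

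The conclusion assumes that the first open-label dose is given at the Week 52 visit, as Protocol 9.1 states. It also assumes that no HRCT-specific rule elsewhere, such as in the TLF shells, already settles the matter.

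**What to change.** **Protocol.** Reconcile the two schedules by amending Section 2.1, footnote 9, with the same change in SAP Appendix 12.1. For subjects entering the Extension, the scan is done from 14 days before the Week 52 visit up to that day, before the first open-label dose. Keep ±2 weeks for all other subjects.

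**SAP.** For scans already taken after the first open-label dose, add one sentence stating how they are assigned to Core Week 52 and to OLE Baseline. Flag them, and repeat the HRCT summary without them.

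**Cost.** One footnote, its copy in the SAP, and one SAP sentence with a repeat summary. No scan is added. The only downside is slightly tighter scan booking for subjects who roll over.

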# 2.2 Schedule of Assessments During the Extension Phase

		Safety Follow-up Visit									
											4 weeks after last dose of fipaxalparant (HZN-825)
Trial Visit	13	14	15	16	17 W74 	18	19 W86 	20 W92	21	22 W104/PD 	23
Trial Week (W) Visit Window (±days)	W52  (±7)	W56	W62	W68 (±7)		W80	(±7)	(±7)	W98 		(114)
Informed consent 4	(±1) X	(±5)	(±7)	(±/)	(±7)	(±7)	(±/)	(±/)	(±7)	(±7)	(±14)
	X										
Review eligibility criteria	X 5					X				X	
Weight Fipaxalparant (HZN-825) dispensing		37	37	37				37		Λ	
	X	X	X	X		X		X			
Compliance	X	X	X	X	X	X	X	X	X	X	
Efficacy Assessments			ı	1					ı		
FVC % predicted/spirometry 	X 5			X		X		X		X	
Titrated oxygen requirement	X 5					X				X	
6MWT	X 5					X				X	
Lung HRCT	X 5									X 7	
DLCO	X 5, 8					X 8				X 8	
Patient-reported Outcome Assessmen											
L-IPF, K-BILD, LCQ, SF-12	X 5					X				X	
Anchor questions											
FVC (last week)	X 5					X				X	
FVC (change since start of trial)						X				X	
Clinical Safety Assessments											
Pregnancy test 	X 5	X	X	X		X		X		X	X
Physical examination 	X 5	X	X	X		X		X		X	X
Vital signs, including pulse oximetry 11	X 5	X	X	X		X		X		X	X
Orthostatic hypotension assessment	X 5	X				X				X	
12-lead electrocardiogram 	X 5	X				X				X	
Echocardiogram 	X 5										
Clinical Laboratory Safety Tests											
Chemistry and hematology 	X 5	X	X	X		X		X		X	X
Fasting glucose and lipids 	X 5					X				X	
hsCRP	X 5					X				X	
Urinalysis 	X 5	X	X	X		X		X		X	X

PRIVATE AND CONFIDENTIAL INFORMATION OF HORIZON THERAPEUTICS IRELAND DAC (A WHOLLY OWNED SUBSIDIARY OF AMGEN INC.)

IND 154671

Fipaxalparant (HZN-825) Protocol: HZNP-HZN-825-303 Version 5.0, Amendment 4

		Open-label Treatment Period											
											4 weeks after last dose of fipaxalparant (HZN-825)		
Trial Visit	13	14	15	16	17	18	19	20	21	22	23		
Trial Week (W)	W52 	W56	W62	W68	W74 	W80	W86 	W92	W98 	W104/PD 			
Visit Window (±days)	(±7)	(±5)	(±7)	(±7)	(±7)	(±7)	(±7)	(±7)	(±7)	(±7)	(±14)		
PK samples 	X 5	X		X		X		X					
Pharmacodynamic serum sample (collect pre-dose) 18	X 5					X				X			
PBMC samples (collect pre-dose) 19	X 5					X				X			
Adverse event assessment	X	X	X	X	X	X	X	X	X	X	X		
Prior/concomitant medications 	X 5	X	X	X	X	X	X	X	X	X	X		

6MWT=6-minute Walk Test; DLCO=diffusing capacity of the lungs for carbon monoxide; FVC=forced vital capacity; HRCT=high-resolution computed tomography; hsCRP=high-sensitivity C-reactive protein; K-BILD=King's Brief Interstitial Lung Disease Questionnaire; LCQ=Leicester Cough Questionnaire; L-IPF=Living with IPF; LPAR1=lysophosphatidic acid receptor 1; PBMC=peripheral blood mononuclear cell; PD=premature discontinuation; PK=pharmacokinetic; SF-12=SF-12® Health Survey; W=Week; WOCBP=women of childbearing potential

- 1. Subjects will receive the first dose of open-label fipaxalparant (HZN-825) in the Extension Phase in the clinic. Baseline assessments will be performed prior to dosing.
- 2. Remote (telephone) visit.
- 3. If a subject prematurely discontinues fipaxalparant (HZN-825), he/she will be asked to remain in the trial, participating in the scheduled trial visits through Week 104. If a subject prematurely discontinues fipaxalparant (HZN-825) and does not wish to continue in the trial, he/she will be asked to return for a clinic visit and undergo the Week 104 assessments. Subjects will return to the clinic 4 weeks after the last dose of fipaxalparant (HZN-825) for a Safety Follow-up Visit.
- 4. Informed consent is required prior to performing any assessments in the Extension Phase. Record date and time informed consent was given and who conducted the process on the appropriate source documentation and per required regulations.
- 5. The result will be considered a Baseline value for this Extension Phase.
- 6. Except when strictly unavoidable, the same person should perform the assessment at each evaluation during the trial.
- 7. The HRCT scan should be performed within ±2 weeks of the Week 104/PD Visit.
- 8. The DLCO is required for Week 80 and Week 104/PD Visits.
- 9. Perform for WOCBP. Serum pregnancy test at Week 104 (or as needed). Urine pregnancy tests should also be done every 4 weeks after the Week 52 Visit, which includes both in-clinic testing at scheduled visits prior to dosing (Weeks 52, 56, 68, 80, and 92) and at home (also a ±7-day window) by the subject and reported to the site (Weeks 60, 64, 72, 76, 84, 88, 96, and 100).
- 10. A complete physical examination will be performed, including, but not limited to, cardiac, pulmonary and neurologic assessments.
- 11. Vital signs (blood pressure, heart rate, respiratory rate, temperature, pulse oximetry) will be measured at each clinic visit. The Week 52 vital sign assessment should be performed before the first dose of open-label fipaxalparant (HZN-825) is administered in the clinic.
- 12. Additional electrocardiograms or echocardiograms will be conducted, if clinically indicated. The Week 52 electrocardiogram should be performed before the first dose of open-label fipaxalparant (HZN-825) is administered in the clinic.
- 13. See Section 9.5.5.9 for details. Samples collected at the Week 52 Visit should be collected before the first dose of open-label fipaxalparant (HZN-825) is administered in the clinic.
- 14. For subjects taking warfarin, physicians should monitor their **INR**, as needed.

Horizon Therapeutics Ireland DAC (a wholly owned subsidiary of Amgen Inc.) Date: 07 October 2024

IND 154671

Fipaxalparant (HZN-825) Protocol: HZNP-HZN-825-303 Version 5.0, Amendment 4

- 15. Includes fasting glucose, total cholesterol, high-density lipoprotein cholesterol, low-density lipoprotein cholesterol, and triglycerides.
- 16. See Section 9.5.5.9 for details.
- 17. PK samples will be collected at each of the following visits: Week 52 (pre-dose), Week 56 (pre-dose and 2 to 4 hours post-dose) and Week 68, 80, 92 (pre-dose). Note: all pre-dose samples will be collected prior to any fipaxalparant (HZN-825) administration for the day.
- 18. To be stored for future analysis. Use of stored serum sample for pharmacodynamic endpoints will be limited to understanding the trial drug as related to investigation of the LPAR1 pathway or disease for the current trial.
- 19. A blood sample for PBMCs will be collected for transcriptomic analysis.
- 20. Includes recording of herb/supplement use. See Table 9.1 for restrictions regarding medications.

# LIST OF ABBREVIATIONS

Abbreviation	Definition	
6MWT	6-Minute Walk Test	
AE	adverse event	
AESI	adverse event of special interest	
ALAT	Latin American Thoracic Society	
ALT	alanine aminotransferase	
AST	aspartate aminotransferase	
ATS	American Thoracic Society	
ATX	autotaxin	
AUC	area under the (plasma) concentration-time curve	
AUC	area under the concentration-time curve from 0 to 12 hours	
BAL	bronchoalveolar lavage	
BID	twice daily	
BP	blood pressure	
CFR Code of Federal Regulations		
CI	confidence interval	
C max maximum observed concentration		
COVID-19 coronavirus disease 2019		
C trough minimum total trough concentration		
CYP cytochrome P450		
DLCO	diffusing capacity of the lungs for carbon monoxide	
DOCA	deoxycorticosterone acetate	
DSUR	Development Safety Update Report	
ECG	electrocardiogram	
eCRF	electronic case report form	
EDC	electronic data capture	
ERS	European Respiratory Society	
EU European Union		
EU CT European Union Clinical Trials		
FAS	full analysis set	
FDA	Food and Drug Administration	
FSH	follicle-stimulating hormone	
FVC	forced vital capacity	

Abbreviation	Definition	
GCP	Good Clinical Practice	
HAQ-DI	Health Assessment Questionnaire – Disability Index	
HBcAb	hepatitis B core antibody	
HBsAb	hepatitis B surface antibody	
HCV	hepatitis C virus	
HRCT	high-resolution computed tomography	
IC 50	half-maximal inhibitory concentration	
ICF	informed consent form	
ICH	International Council for Harmonisation of Technical Requirements for Pharmaceuticals for Human Use	
INR	international normalized ratio	
IDMC	independent data monitoring committee	
ILD	interstitial lung disease	
IND Investigational New Drug		
IPF idiopathic pulmonary fibrosis		
IRT interactive response technology		
JRS	Japanese Respiratory Society	
K-BILD King's Brief Interstitial Lung Disease Questionnaire		
LCQ Leicester Cough Questionnaire		
L-IPF Living with IPF		
LPA lysophosphatidic acid		
LPAR 1	lysophosphatidic acid receptor 1	
MMRM	mixed model for repeated measures	
mRSS	modified Rodnan skin score	
OAT	organic anion transporter	
OLE	open-label extension	
PFS progression-free survival		
PK pharmacokinetic		
QD once daily		
SAE	AE serious adverse event	
SE standard error		
SF-12	SF-12® Health Survey	
SLCO	solute carrier organic anion transporter family member	
SOC	System Organ Class	

Horizon Therapeutics Ireland DAC (a wholly owned subsidiary of Amgen Inc.)

Date: 07 October 2024

Protocol: HZNP-HZN-825-303 IND 154671 Version 5.0, Amendment 4

Abbreviation	Definition
$S_{ m p,O2}$	oxygen saturation
SSc	systemic sclerosis
TEAE	treatment-emergent adverse event
TOR	titrated oxygen requirement
ULN	upper limit of normal
US	United States
WOCBP	women of childbearing potential

Abbreviations that appear only in figures and tables or in a single paragraph are defined with the relevant figures, tables and paragraphs.

Fipaxalparant (HZN-825)

Fipaxalparant (HZN-825) Protocol: HZNP-HZN-825-303 Version 5.0, Amendment 4

